7.1.2 QTc stopping criteria

If a clinically significant finding is identified (including, but not limited to changes from baseline in QT interval corrected using Fridericia's formula [QTcF]) after enrollment, the Investigator or qualified designee will determine if the participant can continue in the study and if any change in participant management is needed. This review of the ECG printed at the time of collection must be documented. Any new clinically relevant finding should be reported as an AE.

A study participant who meets either bulleted criterion based on the average of triplicate ECG readings will be withdrawn from study medication and move into the Observation Period. The study participant should be referred to a specialist (ie, cardiologist) and managed as per local guidance.

- QTc >500 msec OR uncorrected QT >600 msec
- Change from baseline of QTc >60 msec

For participants with underlying bundle branch block, follow the discontinuation criteria listed below:

Baseline QTc with Bundle Branch Block	Discontinuation QTc Threshold with Bundle Branch Block
<450msec	>500msec
450 to 480msec	≥530msec

See the Schedule of Activities for data to be collected at the time of treatment discontinuation and follow-up and for any further evaluations that need to be completed.

7.1.3 Temporary IMP discontinuation

Study participant **must be** TEMPORARILY discontinued from the IMP if any of the following events occur:

1. The study participant develops an event of hypogammaglobulinemia with a serum total IgG of <1g/L irrespective of infection. When the IgG level reaches ≥2g/L, the study participant may be allowed to continue treatment with IMP (see Appendix 13; Section 10.13.1).
2. Symptomatic cases of confirmed COVID-19 infection. The IMP may be restarted if clinically appropriate when signs and symptoms have resolved and in agreement with local guidelines.
3. Study participant has a suspected DIAM. The IMP may be restarted if clinically appropriate when signs and symptoms have resolved. Refer to Section 7.1.4 for permanent discontinuation criteria (criterion #10).

Study participants **may be** TEMPORARILY discontinued from the IMP if the following events occur:

1. The study participant develops a nonserious persisting or recurrent infection with serum total IgG level between ≥1 and <2g/L. Upon resolution of infection and the IgG returning to level of ≥2g/L, the study participant may be allowed to resume treatment with the IMP (see Appendix 13; Section 10.13.1).
2. Asymptomatic or suspected cases of COVID-19 infection. The IMP may be restarted when clinically appropriate as deemed by the Investigator and in agreement with local guidelines.
3. Study participant has a moderate to severe infection (Grade 2 to 3) that may or may not result in hospitalization, unless the **discontinuation criterion #3** is met. Decision to start a new treatment cycle should be based on careful evaluation by the Principal Investigator of the Benefit-Risk for the individual study participant and provided a full recovery from infection has occurred, an acceptable level of total IgG (≥2g/L) has been reached and no other discontinuation criteria were met.

The Investigator should discuss with the Medical Monitor and/or Sponsor's study physician prior to reinitiating the IMP. As appropriate, virtual assessments could continue (eg, AE collection, patient-reported outcome [PRO] assessments as per contingency measures described in Section 8).

If IMP treatment is resumed, continue the next dose as previously scheduled. No "make up" dose is permitted.

The participant should subsequently follow the visit schedule as described in the protocol, and the eCRF should be completed accordingly, including the information if the visit was impacted by COVID-19 infection.

The date and reason for dose modification/hold of rozanolixizumab is to be recorded on each study participant's eCRF.

7.1.4 Study medication permanent discontinuation criteria

Study participants **must** permanently discontinue study medication if any of the following events occur:

1. Study participant develops an illness that would interfere with his or her continued participation.
2. Study participant has new onset or recurrent neoplastic disease (except for superficial basal or squamous cell carcinoma of the skin not requiring targeted biological therapy, chemotherapy or radiation).
3. Study participant experiences a significant infective episode including but not limited to bacteremia/sepsis, infectious meningitis, septic arthritis, osteomyelitis, complicated pneumonia, or visceral abscess, which may or may not result in hospitalization during a treatment period. This list is not intended to be all inclusive and the investigator is expected to apply his/her judgement on continuing IMP based on the clinical situation.

However, if a significant infective episode is reported during observation and no treatment with rozanolixizumab period, the decision to start a new treatment cycle should be based on careful evaluation by the Principal Investigator of the Benefit-Risk for the individual study participant and provided a full recovery from infection, an acceptable level of total IgG ($\geq 2\text{g/L}$) and no other discontinuation criteria were met.

4. Study participant meets potential drug-induced liver injury (PDILI) permanent discontinuation criteria.
5. Study participant has a TB test that is confirmed positive or any further evidence suggestive of potential TB infection (ie, exposure) and further examinations result in a diagnosis of active TB or latent TB infection (LTBI).
6. If a nontuberculosis mycobacterium infection (NTMBI) is identified during a study, the same withdrawal procedures as those used for an active TB infection identified during the study should be followed.
7. Removed.
8. Study participant has an AE of severe or serious infusion or anaphylactic reaction requiring corticosteroid and/or epinephrine therapy (Sampson et al, 2006).
9. Study participant is treated with rescue therapy (IVIg, SCIG, PEX, or iv corticosteroids; see Section 6.5.4) during the Treatment Period. Those patients who received rescue therapy during the observation or no treatment with rozanolixizumab periods may continue in the study at the investigator's discretion and after discussion with Medical Monitor and/or UCB Study Physician. The following cycle of rozanolixizumab should in general not start earlier than 4 weeks following the last dose of IVIg, SCIG, or iv corticosteroids or the last PEX

session, unless there is a medical reason, and an earlier treatment initiation is being considered █ for the study participant as agreed upon with the Medical Monitor and/or UCB Study physician.

10. Study participant has a recurrence of aseptic meningitis (see also Appendix 14 [Section 10.14]).

Study participants **may** permanently discontinue rozanolixizumab **and** move into the Observation Period at the discretion of the Investigator, Medical Monitor, and Study Physician if any of the following events occur:

1. Study participant is noncompliant with the study procedures or medications in the opinion of the Investigator.
2. Study participant takes prohibited concomitant medications as defined in this protocol.

Investigators should contact the Medical Monitor, whenever possible, to discuss the withdrawal of a participant in advance. Investigators should attempt to obtain information on study participants in the event of withdrawal (eg, reason for withdrawal, any safety information).

In the event of study participant early withdrawal, the scenarios as described in Section 4.4 need to be considered.

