10.13.1 Management of infections and hypogammaglobulinemia

Study participants who have signs or symptoms of any infection should be monitored closely and managed according to local guidelines. This may include tests for specific organisms if clinically indicated.

Study participants **MUST discontinue IMP AND move into the SFU Period** if he/she develop a significant infective episode including but not limited to bacteremia/sepsis, infectious meningitis, or septic arthritis, osteomyelitis, complicated pneumonia, or visceral abscess which may or may not result in hospitalization during a treatment period.

If a significant infective episode is reported during observation period, the decision to start a new treatment cycle should be based on careful evaluation by the Principal Investigator of the Benefit-Risk for the individual study participant and provided a full recovery from infection, an acceptable level of total IgG ($\geq 2\text{g/L}$) and no other discontinuation criteria were met.

To maintain the study integrity, IgG level will remain blinded to the study sites and the UCB study team for the first 4 weeks of the study. To ensure patient safety, serum IgG level will be monitored by an independent Medical Monitor external to UCB including signs and symptoms of infection and associated laboratory parameters. The IMP may be temporarily discontinued as requested by the independent Medical Monitor when deemed appropriate.

In the event of a non-serious infection, the Benefit-Risk of continuing treatment with IMP must be carefully evaluated by the Investigator in collaboration with the Medical Monitor. Treatment may be temporarily discontinued for the study participant who develops a non-serious persisting or recurrent infection with a serum total IgG level between $\geq 1\text{g/L}$ and $< 2\text{g/L}$. Upon resolution of infection and the IgGs returning to the level of $\geq 2\text{g/L}$, the study participant may be allowed to resume treatment with the IMP. Ad hoc assessment can be performed to monitor the recovery of IgG levels.

Treatment must be temporarily discontinued for the study participant who develops an event of hypogammaglobulinemia with a serum total IgG of $< 1\text{g/L}$ irrespective of infection. When the IgG level reaches $\geq 2\text{g/L}$, the study participant may be allowed to continue treatment with IMP.

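### For a significant infection during a treatment cycle, Protocol 7.1.4 and Section 10.13.1 disagree on whether stopping IMP is open to judgement, and 10.13.1 sends the participant to a period the plan does not define

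*Protocol*

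**What the plan says.** Protocol 7.1.4 opens with a mandatory instruction: participants must "permanently discontinue study medication if any of the following events occur". Criterion 3 on that list reads "Study participant experiences a significant infective episode including but not limited to bacteremia/sepsis, infectious meningitis, septic arthritis, osteomyelitis, complicated pneumonia, or visceral abscess", and applies to episodes during a treatment period. It goes on to say that the list of examples is not exhaustive and, in the same sentence, that "the investigator is expected to apply his/her judgement on continuing IMP based on the clinical situation".

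Section 10.13.1 in Appendix 13 deals with the same episodes, again during a treatment period. Its instruction is that participants "MUST discontinue IMP AND move into the SFU Period".

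For episodes between cycles, both sections replace the stop rule with a benefit-risk decision on starting a new cycle. In 7.1.4 this applies "if a significant infective episode is reported during observation and no treatment with rozanolixizumab period"; in 10.13.1 the text is "If a significant infective episode is reported during observation period".

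Section 7.1.3 adds an optional temporary hold, for the case "Study participant has a moderate to severe infection (Grade 2 to 3) that may or may not result in hospitalization", unless discontinuation criterion 3 is met.

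**The concern.** Serious infection is one of the two safety concerns named in Protocol 2.3. A mandatory stop rule for it should read the same wherever a site finds it. Here a site reading 7.1.4 sees a mandatory, permanent stop followed by a sentence about judgement on continuing. A site reading 10.13.1 sees a mandatory stop with no such sentence, and then an instruction that cannot be followed because the destination is not defined.

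The statistical stake is classification. TEAEs leading to withdrawal of IMP is a primary safety endpoint (Protocol 3; SAP 2.2.1.1), and SAP 8.2.2 tabulates permanent and temporary withdrawal of IMP separately. The same infection could be reported as a permanent withdrawal, as a temporary one, or as neither, depending on how the site read the rule.

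**Working it through.** There is no figure in the plan to reproduce on this point, so the check is a comparison of the texts.

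| Question | Protocol 7.1.4, criterion 3 | Protocol 10.13.1 |
|---|---|---|
| Trigger | Significant infective episode in a treatment period; six examples, open list | Same six examples, open list, same period |
| Force | Mandatory and permanent, from the lead-in | Mandatory; permanence not stated |
| Judgement on continuing | Yes, in the criterion itself | None |
| What follows the stop | No period named; pointer to Section 4.4 for early withdrawal | SFU Period |
| Between-cycle decision covers | Observation and no-treatment periods | Observation period |

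**Force.** The judgement clause in 7.1.4 speaks of continuing IMP, which is the opposite of what the lead-in requires. Nothing in the wording confines it to unlisted infections. Even if it were so confined, the list in 10.13.1 is open too. An unlisted but significant infection would then be open to judgement under 7.1.4 and subject to a mandatory stop under 10.13.1.

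**Which section governs.** Section 8.3.7 says suspected infections are to be managed under Appendix 13, and 7.1.3 also refers to 10.13.1. We found no statement of which text prevails, so sites are sent to both.

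**Destination.** The SFU Period is absent from the Schedule of Activities (Tables 1-2 to 1-5), from Section 4.4 and from the abbreviations in Appendix 9. SAP 3.2.2 defines only Treatment, Observation and Non-treatment periods. Section 7.1.4 names a destination, the Observation Period, only for its two optional criteria. For the mandatory ones it offers the pointer to Section 4.4, where a participant still in a cycle must complete that cycle and then the first 8 weeks of the Observation Period before the EOS visit. That can be read as attending the remaining visits without dosing, but Section 4.4 does not say so, and completing the cycle sits badly with a stop of the drug.

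**Consequence for the data.** TEAE counting is not affected by the missing period, because the 56-day window in SAP 8.2.1 is anchored to the last dose. Visit-based data are more exposed: SAP 3.2.1 analyses by the visits in the Schedule of Activities, and no SFU visits exist there.

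**Temporary hold.** Both 7.1.3 and criterion 3 apply whether or not the participant is hospitalized, so hospitalization does not separate them. The dividing line is whether criterion 3 is met, and so it inherits any doubt about criterion 3.

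**The case against.** The best defence starts from the full sentence in 7.1.4. The judgement clause follows directly on the statement that the list is not exhaustive, so the natural intent may be that listed infections always stop the drug and the investigator decides on the others. That reading is plausible, and it makes the internal problem in 7.1.4 an ambiguity rather than a flat contradiction. It does not dispose of the point, because the words do not carry that limit and 10.13.1 has no matching clause.

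Several stronger inferences are open to a reader, and the documents do not support them:

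- **That 10.13.1 makes the stop non-permanent by omitting the word.** This is weak. Elsewhere that section says temporary when it means a hold, so its unqualified instruction reads as the contrast. Like 7.1.4, it offers retreatment only for episodes reported off treatment.
- **That two follow-up schedules compete.** They do not. Section 7.1.4 names no rival period for criterion 3. Where other text names a period after a drug stop (7.1.2 for QTc, the optional criteria in 7.1.4), it is the Observation Period, and Tables 1-2 and 1-3 show that period straight after treatment. SFU may simply be a stray label for it. The defect is an undefined term plus a pointer that fits poorly.
- **That criterion 3 exists in two versions, which shift the boundary with 7.1.3.** Only 7.1.4 has numbered discontinuation criteria, so the cross-reference has one target.
- **That the primary endpoint would move by a stated number of percentage points or standard errors.** The documents give no rate for such infections or for IMP withdrawal. All analyses are descriptive (SAP 4.1 and 4.6), so a comparison with a standard error would decide nothing.

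Two mitigating facts also stand. Section 7.1.4 asks investigators to contact the Medical Monitor before a withdrawal whenever possible, which limits divergence between sites. And because SAP 8.2.2 reports temporary withdrawals too, a held participant is not lost from the tables. The narrower list of periods in 10.13.1 contradicts nothing outright, since 7.1.4 covers the no-treatment period, so that mismatch is minor.

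**Conclusion.** The point holds as an internal inconsistency in a mandatory stop rule. Both sections start from discontinuation of IMP for a significant infection during treatment. They differ on whether investigator judgement applies, and the only period named for what follows is undefined. The different lists of periods in the between-cycle rule are a lesser mismatch.

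The effect on the primary endpoint cannot be sized from the documents. What can be said is that the classification of an individual infection as permanent withdrawal, temporary withdrawal or neither depends on the reading. A reader might also take withdrawal to mean leaving the study. It does not: significant infection is not among the mandatory study-withdrawal events in Protocol 7.2.

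The finding that the SFU Period is undefined rests on the text and tables supplied; the schema figures could not be seen.

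**What to change.** Reconcile Protocol 7.1.4 (criterion 3 and the closing pointer to Section 4.4), Section 4.4 and Section 10.13.1:

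1. State once whether the stop is mandatory and permanent or subject to judgement and, if judgement applies, to which infections. Have 10.13.1 refer to that statement rather than restate it.
2. Replace the SFU Period with a period and visit schedule that exist in Tables 1-2 and 1-3, and say in Section 4.4 how its rule applies to a participant whose IMP has been stopped mid-cycle.
3. Use the same list of periods for the between-cycle retreatment decision in both sections.

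The cross-reference in 7.1.3 then follows the reconciled criterion 3 and needs no separate rule. Which clinical rule to adopt is for the sponsor. The cost is protocol wording in these sections, with no new procedures.

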8.3.7 Adverse events of special monitoring

An AE of special monitoring (AESM) is a product-specific AE, adverse reaction, or safety topic requiring special monitoring by UCB.

For rozanolixizumab, the following events require immediate reporting (within 24 hours regardless of seriousness) to UCB:

- Severe and/or serious headache
- Suspected aseptic meningitis

Procedures for the management of AESM are provided in Appendix 14 (Section 10.14).

Although infections and infusion-related reactions as well as hypersensitivity reactions or anaphylaxis are not classified as AESM, these AEs will be monitored by the Investigator. If such an event is suspected it should be managed according to the guidance provided in Appendix 13 (Section 10.13). In case of suspected anaphylaxis, the Sampson's Criteria (Sampson et al, 2006) in Appendix 15 (Section 10.15) should be completed.

All AESM will follow the SAE recording and reporting procedures as indicated in Appendix 3 (Section 10.3).

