10.13.2 Management of infusion reactions or hypersensitivity reactions

Study participants must be closely monitored for reactions during and after the study treatment administration period. Standard precautions must be taken for the study participants with regard to sc infusion complications. Suggested management guidelines for infusion-related reactions and anaphylaxis at the study site are provided in **Table 10-3**. Definitions of mild, moderate, and severe events will be consistent with CTCAE version 5.0 (Section 10.3).

Nurses administering the IMP at home should follow their own management guidelines, which should be reviewed and endorsed by the Investigator prior to first home administration.

Table 10-3: Suggested management guidelines for infusion reactions or anaphylaxis

Type of reaction	Suggested action
Acute – Mild Grade 1	Monitor vital signs every 10 min. If the reaction worsens to Grade 2, follow the instruction below.
Acute – Moderate Grade 2	Interrupt/hold infusion temporarily to further assess and initiate treatment if necessary. Consider the use of iv fluid and antihistamine iv/im. Consider administering paracetamol or NSAIDs. Monitor vital signs initially every 5 min. If the reaction improves and upon further assessment it is clear that the event is not an anaphylaxis, restart the infusion cautiously. Continue monitor vital signs every 5 minutes. If reaction recurs or worsens to Grade 3, discontinue infusion.
Acute – Severe Grade 3 or anaphylaxis	Discontinue IMP infusion permanently. Emergency care services. Maintain airway; ensure oxygen is available. Administer: 
– Antihistamine iv/im, corticosteroids iv, epinephrine im, and iv fluids as appropriate.– Monitor vital signs every 2 min.– Hospitalize, if condition not improving or worsens– Monitor patient until symptoms resolve.

CTCAE=Common Terminology Criteria for Adverse Events; im=intramuscular; IMP=investigational medicinal product; iv=intravenous(ly); NSAID=nonsteroidal anti-inflammatory drug

Note: Management criteria were adapted from the CTCAE v5.0 (National Cancer Institute, 2017).

Conditions in which anaphylaxis is likely should be diagnosed using Sampson's Criteria (Sampson et al, 2006. The infusion must be discontinued immediately, and emergency resuscitation measures implemented.

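### Protocol 7.1.4 criterion 8 and Table 10-3 give different triggers for permanent discontinuation after an infusion or anaphylactic reaction

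*Protocol*

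**What the plan says.** Section 7.1.4 lists events after which participants must "permanently discontinue study medication if any of the following events occur". Criterion 8 in that list is: "Study participant has an AE of severe or serious infusion or anaphylactic reaction requiring corticosteroid and/or epinephrine therapy". It names two conditions: how bad the reaction is (severe or serious) and what treatment it required.

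Section 8.3.7 says of infusion-related reactions, hypersensitivity and anaphylaxis: "If such an event is suspected it should be managed according to the guidance provided in Appendix 13". Within that appendix, section 10.13.2 introduces its table with the words "Suggested management guidelines for infusion-related reactions and anaphylaxis at the study site are provided in" Table 10-3. Three entries matter here:

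- **Grade 3 or anaphylaxis row:** "Discontinue IMP infusion permanently". The drugs named in criterion 8 appear in this row as treatment, not as a condition: "Antihistamine iv/im, corticosteroids iv, epinephrine im, and iv fluids as appropriate".
- **Grade 2 row, improvement:** "If the reaction improves and upon further assessment it is clear that the event is not an anaphylaxis, restart the infusion cautiously".
- **Grade 2 row, recurrence or worsening:** "If reaction recurs or worsens to Grade 3, discontinue infusion". The word permanently is absent here.

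TEAEs leading to withdrawal of IMP is one of the two primary safety endpoints (Protocol section 3; SAP 2.2.1.1). SAP 8.2.2 tabulates permanent and temporary withdrawal of IMP separately.

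**The concern.** Two passages tell a site when a reaction ends treatment for good, and they use different tests. Criterion 8 turns on severity or seriousness together with corticosteroid or epinephrine. Table 10-3 turns on grade or the diagnosis of anaphylaxis alone. Neither refers to the other or says which prevails.

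The protocol does align comparable rules elsewhere. Section 7.1.3 points to Appendix 13 for the IgG and infection holds, criterion 10 of 7.1.4 points to Appendix 14, and section 10.13.1 restates the infection trigger of criterion 3. Infusion reactions have no such link.

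Two things are at stake. First, section 2.3 names hypersensitivity reactions as a safety concern, and participants with the same reaction could be managed differently. Second, a difference in handling carries into the count of TEAEs leading to withdrawal of IMP and into the SAP's split between permanent and temporary withdrawal.

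**Working it through.** The plan states no figure on this point, so there is none to reproduce. The check sets the two rules side by side over the features they use, then scales one participant's effect on the endpoint.

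**Step 1. Code the rules.** Severe is taken as Grade 3, since 10.13.2 ties severity to CTCAE. Seriousness is a separate attribute under Appendix 3, so a Grade 2 event can be serious. Treated means that corticosteroid and/or epinephrine was required.

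- Criterion 8 requires a stop if (Grade 3 or serious) and treated.
- Table 10-3 says stop permanently if Grade 3 or anaphylaxis.

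**Step 2. Compare them** over grade (2 or 3), serious (yes or no), anaphylaxis (yes or no) and treated (yes or no): 2 × 2 × 2 × 2 = 16 combinations.

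| Reaction | Combinations | Criterion 8 | Table 10-3 | Same? |
|---|---|---|---|---|
| Grade 3, treated | 4 | must stop | stop | yes |
| Grade 3, not treated | 4 | silent | stop | no |
| Grade 2 anaphylaxis, serious, treated | 1 | must stop | stop | yes |
| Grade 2 anaphylaxis, serious, not treated | 1 | silent | stop | no |
| Grade 2 anaphylaxis, not serious | 2 | silent | stop | no |
| Grade 2, not anaphylaxis, serious, treated | 1 | must stop | restart allowed | no |
| Grade 2, not anaphylaxis, serious, not treated | 1 | silent | restart allowed | yes |
| Grade 2, not anaphylaxis, not serious | 2 | silent | restart allowed | yes |

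The rules differ in 4 + 1 + 2 + 1 = 8 of 16. In 7 of the 8 the table says stop and criterion 8 is silent. In 1 criterion 8 says must stop and the table allows a restart. These are logical combinations, not expected patients.

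**Step 3. Test the other reading of criterion 8.** The treatment condition could attach only to anaphylactic reactions. Grade 3 infusion reactions then agree. Anaphylaxis not needing those drugs, and non-serious Grade 2 anaphylaxis, still differ (2 + 1 + 2 = 5 combinations). Serious Grade 2 non-anaphylactic reactions also differ, treated or not (2 combinations). That is 7 of 16, so the mismatch survives either reading.

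**Step 4. Scale the endpoint.** Planned enrolment is about 200 (Protocol 9.8). One participant counted differently moves the percentage by 1/200 = 0.5 points, or by 1/100 = 1.0 point within a dose group if the groups are assumed equal. For an assumed 1 to 5 participants, all in the same direction, the overall range is 0.5 to 2.5 points. The two types of mismatch have opposite signs: relative to criterion 8, the table adds untreated Grade 3 cases and removes treated serious Grade 2 cases. A mixture would partly cancel.

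**The case against.** The strongest reply is that a mandatory minimum sits beside broader advice, which is not a contradiction. Section 7.1.4 says when stopping is compulsory. It does not say that dosing continues otherwise. A site that follows Table 10-3 for an untreated Grade 3 reaction breaches nothing in 7.1.4. Section 7.2 also permits withdrawal for safety at the Investigator's discretion, and section 8 requires immediate safety concerns to be discussed with the sponsor. This stands, and it covers 7 of the 8 differing combinations. A reader might infer that the protocol orders permanent withdrawal on one page and further dosing on another for the same Grade 3 reaction. The documents do not support that, because no passage directs re-exposure in those cases.

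Second, the wording ranks the two passages: a compulsory list against suggested guidelines, with home nurses told to use their own guidelines endorsed by the Investigator. This is fair as to status. It does not remove the problem, because 8.3.7 sends sites to that appendix, and the table's own word is permanently.

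Third, the table may govern only the acute handling of one infusion. Its object is the IMP infusion, and permanently may simply contrast with the temporary hold in the Grade 2 row. That reading is possible. It would leave the table with no rule on study medication at all, so the text needs clarifying either way.

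Fourth, the direct conflict needs a serious Grade 2 non-anaphylactic reaction that required corticosteroid or epinephrine and then improved. The Grade 2 row lists neither drug, so such a case is probably uncommon. Restarting one infusion also does not cancel the compulsory stop in 7.1.4. This stands, and it is why the conflict is described as narrow.

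**Conclusion.** The two triggers differ, and the passages should be reconciled. The consequence is limited to three things: uncertainty over whether a permanent stop is mandatory for Grade 3 reactions or anaphylaxis managed without corticosteroid or epinephrine; one narrow direct conflict at serious, treated, non-anaphylactic Grade 2; and an unclear meaning of permanently in Table 10-3.

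The effect on the withdrawal endpoint is 0.5 points per participant handled differently, resting on the planned figure of about 200. The endpoint is reported on the Safety Set, so a smaller treated number would make each participant count for slightly more. A reader might go on to quote a total shift, or a fraction of a standard error, by assuming a number of reactions and a background withdrawal rate. The documents give neither, and opposite-signed cases would offset, so no total can be stated. The analysis is descriptive with no testing planned (SAP 4.1 and 4.6), so no error rate or power is affected.

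A reader might also infer that the SAP should tie the endpoint to the chosen trigger. It should not: the endpoint counts TEAEs that actually led to withdrawal of IMP, not criteria met, and tying it to a trigger would exclude genuine discretionary withdrawals.

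**What to change.** The sponsor should reconcile 7.1.4 criterion 8 and Table 10-3 so that the same permanent-discontinuation trigger (grade, seriousness, and any treatment condition) appears in both. Table 10-3 should cross-refer to 7.1.4 and state whether permanently refers to study medication or to the infusion in progress. The Grade 2 row, including its line on recurrence or worsening, should be made consistent with that trigger. Which trigger applies is for the sponsor to decide; no view is offered here.

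The cost is protocol wording in two places and a notice to sites. No procedures are added and no SAP change is needed.
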